## Protocol Summary

- Full Title:** *Is it Feasible?: Self-Affirmation for Hereditary Breast and Ovarian Cancer Genetic Counseling*
- Principal Investigator:** *[name]*
- Sample Size:** *N= 74, patient control group =35, patient treatment group = 35, genetic counselors =4*
- Accrual Ceiling:** *180 participants*
- Study Population:** *Clients being seen for an initial visit in the hereditary breast and ovarian cancer (HBOC) clinic, both affected and unaffected with cancer, female, 18-90 years-old*
- Accrual Period:** *July 2017 – February 2017*
- Study Design:** *This study is a feasibility study to assess the acceptance and initial outcomes of a self-affirmation intervention in a novel HBOC genetic counseling context. The study relies on surveys of 4 genetic counselors and 70 clients after a small case control study. The purpose is to estimate effect sizes and preliminary outcomes of self-affirmation in a genetic counseling setting and to assess client and counselor interest in self-affirmation interventions.*
- Study Duration:** Start Date: *June 2017* End Date: *March 2017*
- Primary Objective:** *To identify outcomes that may be applicable for a larger SA intervention study in the genetic counseling context by randomly assigning clients to a control or intervention arm and then surveying them after the SA intervention and genetic counseling appointment.  
To assess clients' and counselors' opinions of an SA intervention by post study surveys.*
- Secondary Objectives:** *To assess process outcomes of a SA intervention including the time required to complete the intervention, uptake, and attrition.*
- Endpoints:** *Client's completion of follow-up survey; Counselor's completion of study review survey.*

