Appendix C) (Creswell et al., 2013; Havranek et al., 2012). They will then be asked to write about the item that is most important to them and why it may be important to them. The control group will rank the same list and be asked to write about the 9th ranked item and why it might be important to someone else. The control condition is consistent with the control used in other SA intervention studies. The 9th ranked item is chosen to inhibit a reverse effect where participants feel affirmed because they do not value something that is aversive to them. Both the intervention and control group will receive a 6-question survey of state anxiety along with the writing prompt, which will be used as a control measure.

Potential participants will be identified through the patient schedule and will be contacted by the student assistant investigator (AI), [name], about one week prior to their appointment to invite them to participate in the study and obtain verbal informed consent. Participants will be recommended to arrive 15 minutes prior to their scheduled appointment. When clients arrive at the HBOC clinic, the front desk staff will give client participants the SA or control intervention based on random assignment. The affirmation intervention or control condition will be completed directly before the regularly scheduled appointment.

Genetic counselors will be blinded to the study condition of their clients, although clients might choose to discuss the content of the intervention survey with the counselor. Counseling sessions will otherwise proceed according to protocol for the clinic. Clients will receive a paper survey as they leave the appointment regarding their demographic information (age, sex, education, race, ethnicity, cancer status) experience in the study, decision self-efficacy, empowerment, genetic knowledge, intentions to talk with family, information seeking, and intentions to pursue genetic testing if it was offered. They will be given the option to fill out the paper version or to access an electronic version online. Hard copy surveys will be returned to the front desk or by mail to the AI. Electronic versions will be sent to an email address provided by the client. A week after their appointment, all clients will receive an electronic reminder notification to complete the questionnaire. Upon completion of the online survey or paper questionnaire participants will be mailed a \$15 gift card.

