### **Responsibilities of St. Luke's Health System and Medstar Washington Hospital Center**

[name] and [name] are genetic counselors at St. Luke's Health System and non-NIH collaborators for this research study. The St. Luke's Health system HBOC scheduling coordinator will distribute and collect the intervention, client surveys, and contact cards on site at the St. Luke's health system HBOC clinic. The scheduling coordinator will also collect the genetic counselor after visit and end of study surveys. They will mail all deidentified materials to the NIH researchers for analysis.

[name] and [name] are the genetic counselors at Medstar Washington Hospital Center and non-NIH collaborators for this research study. Similarly to St. Luke's Health System, the front desk personnel will distribute and collect the study intervention, client surveys,

and contact cards. Because this clinic does not have one assigned clinic coordinator, the counselors will confirm and oversee that study materials are appropriately returned to the AI.

The intervention and client survey will not include identifying information and contact information will be separated from the other study materials. All surveys and the intervention are self-administered.

- 5.1 N/A
- 5.2 N/A
- 5.3 N/A
- 5.4 N/A
- 5.5 N/A
- 5.6 Describe questionnaires or other psychological instruments and estimate how long they will take to complete, and whether they address sensitive topics (Appendix C-F)

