### **Intervention (See appendix C)**

For the SA intervention, participants will be asked to rank 11 items (artistic skills, athletics, business/money, creativity, independence, music, politics, relationships with friends and family, religious values, sense of humor, spontaneity) from most important to least important (Creswell et al., 2013; Havranek et al., 2012). They will then be asked to write about the item that is most important to them and why it may be important to them. The control group will rank the same list and be asked to will write about the 9th ranked item and why it might be important to someone else. The control condition is consistent with the control used in other SA intervention studies.

Immediately after the intervention or control condition, participants will complete a 2 minute survey that consists of the short version of the Stat-Trait Anxiety Inventory (STAI). This measurement entails 6 questions to assess the client's current anxiety. The purpose of the STAI is to control for anxiety, to identify if those who are more anxious are more effected by the SA intervention. The intervention and STAI should take about 10-15 minutes together. At the end of the intervention there will be a detachable page asking for the client's email address to send them with the post-intervention survey and a reminder to complete it. This document will be immediately separated from the study material by the scheduling coordinator.

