This aim will be analyzed as percent of yes/no response to intervention survey questions for both clients and counselors. There will also be open ended questions for specific impacts, barriers, and facilitators to be mentioned, which will be analyzed using thematic analysis of answers. The AI will create a codebook based on initial read through and subsequently code all answers. A separate coder will validate ten percent of answers for consistency.

Aim 3: To assess the percentage of clients that completed a pre-visit SA intervention among client participants and if the SA intervention is affective in affirming clients.

Intervention uptake will be reported as a percentage of participants who were eligible based on counselor referral and who were contacted by AI that completed the SA intervention and client survey. Effectiveness of affirmation is an internal control and will be assessed by screening the last question on the intervention for those in the intervention group who report higher than a 2 and those in the control group who report lower than a 5. Additionally, transcripts of intervention essays will be analyzed for affirmation themes.

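### Time to complete the intervention is a secondary objective, but no described procedure records it and no planned analysis uses it

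*Combined protocol and SAP*

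**What the plan says.** The Protocol Summary states the secondary objective as "To assess process outcomes of a SA intervention including the time required to complete the intervention, uptake, and attrition". Completion time is the first process outcome it names.

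On conduct, Section 5.0 says that "the front desk staff will give client participants the SA or control intervention based on random assignment", and that "Participants will be recommended to arrive 15 minutes prior to their scheduled appointment". The site responsibilities add that "All surveys and the intervention are self-administered", and that the St. Luke's scheduling coordinator "will distribute and collect the intervention, client surveys, and contact cards on site"; front desk personnel do the same at Medstar.

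On duration, the Intervention part of Section 5.6 says "The intervention and STAI should take about 10-15 minutes together". It allots two minutes of that to the six-question STAI.

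On analysis, Section 7.0 under Aim 3 covers uptake ("Intervention uptake will be reported as a percentage of participants who were eligible", continuing with referral and contact by the associate investigator) and whether the affirmation worked. It does not mention time.

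**The concern.** This is a feasibility study, and Section 3.0 justifies it partly by the need to learn about logistics and barriers. Whether the writing task fits into the wait before a clinic appointment is one of the plainest logistical questions. The plan assumes that it fits: the upper end of the estimated duration equals the recommended early arrival. An objective with no measurement and no analysis cannot be answered at the end, and times that were never written down cannot be recovered later.

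Reasons for non-completion are also at stake. A client who does not want to do the exercise and a client who is called in halfway through are different barriers, and a larger trial would address them differently. The STAI follows the task, and Section 7.0 takes its affirmation rating from the last question on the intervention. Interruption would therefore tend to cost exactly those two items, which are covariates in the Aim 1 regressions for decision self-efficacy, empowerment and knowledge.

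**Working it through.** **Step 1. Look for completion time wherever it could be recorded or analysed.**

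- Protocol Summary, secondary objective: named. Protocol Summary, endpoints: client follow-up survey and counselor review survey only.
- Section 2.0, specific aims: not mentioned. Aim 3 covers the percentage completing and whether the intervention affirms.
- Section 5.0 and site responsibilities: hand-out, self-completion, collection. No start time, stop time or staff log is described.
- Section 5.6, intervention packet: ranking, writing, six STAI items, detachable email page. Section 7.0 adds a last question on affirmation. No time field is described.
- Section 5.6, client post-intervention survey: outcome measures, plus open-ended and yes/no items on response to the exercise. Section 5.0 adds demographics. No time item is described.
- Section 5.6, counselor after-visit survey: the counselor version of the 24-item GCOS. No time item is described.
- Section 5.6, counselor post-study survey: four yes/no questions with open-ended follow-up, one Likert item, free comments. No time item is described.
- Section 7.0: uptake is given an analysis as a percentage; time is given none.

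Time therefore appears as an objective once, and nowhere in the described measurement or analysis.

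**Step 2. What the plan's own figures imply.** The 10-15 minutes is a planning estimate with no formula behind it, so there is nothing to reproduce. Inputs: 10-15 minutes for intervention plus STAI and 2 minutes for the STAI (Section 5.6); 15 minutes of early arrival (Section 5.0).

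- Task alone = total minus STAI: 10 − 2 = 8 to 15 − 2 = 13 minutes.
- Slack = early arrival minus total: 15 − 15 = 0 to 15 − 10 = 5 minutes.

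The slack treats an approximate duration and a recommended arrival as exact, and allows nothing for check-in or late arrival. It shows how tight the plan is; it does not predict how many clients will overrun.

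**Step 3. What recorded times would buy.** Suppose all 35 clients in the self-affirmation arm have a time, and let p be the proportion finishing within 15 minutes. The documents give no value for p, so it is assumed. The approximate 95% half-width is 1.96 × √(p(1 − p)/35).

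- p = 0.5: 1.96 × √(0.25/35) = 0.17
- p = 0.8: 1.96 × √(0.16/35) = 0.13
- p = 0.9: 1.96 × √(0.09/35) = 0.10

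About ±10 to ±17 points over this range is coarse, but usable for planning the arrival window of a larger trial.

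**The case against.** The strongest objection is that the forms themselves are out of sight. Section 5.6 refers to Appendices C to F, and none is in the text at hand. A start and stop field, or a question on how long the exercise took, could be printed there. A reader might infer that no client will contribute a time; the documents do not support that as a certainty. What stands is that no such field is described and that Section 7.0 would leave it unanalysed even if it existed.

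A reader might also infer that a client called in mid-task leaves no trace. That is wrong. The packet is collected, and a half-written essay or blank STAI would be visible and would differ from an untouched form. What is not systematically recorded is the reason.

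Nor is it right that the plan can learn nothing about time pressure. Aim 2 asks about barriers, clients are asked whether and how the exercise affected their session, and counselors have open-ended items. These could bring up time pressure, but only as anecdote. They give no duration and no proportion.

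Finally, time appears only in the Protocol Summary, so this may be a mismatch between summary and body. That is a fair reading, but it does not remove the problem: the stated objective has to be either measured or withdrawn.

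**Conclusion.** The point holds as a gap between a stated objective and the described plan. Completion time is a secondary objective with no described measurement and no analysis. The absence of an analysis is certain from Section 7.0. The absence of data rests on one assumption, that the appendix forms hold no time field. If so, the study ends with its planning estimate and no observed distribution to set against it.

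That estimate should not be read as 10-15 minutes for the intervention alone, because it includes the STAI. No Aim 1 comparison is invalidated by this gap; any effect through missing covariates is possible, but its size cannot be judged from the documents. It is best classed as a cheap improvement, worth making while recruitment continues because it cannot be made afterwards.

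**What to change.** Add two clock times to the packet, written by the client at the start of the ranking task and at the end of the writing task. Failing that, have the front desk note hand-out and return times. In either case add a front-desk tick-box for clients called to the appointment before finishing.

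In Section 7.0 under Aim 3, report by arm the median and interquartile range of completion time, the percentage over 15 minutes and the percentage interrupted, with the number of clients lacking a time. If the times cover only ranking and writing, say so beside the 15-minute cut-off, since the STAI must fit into the same wait. If only hand-out and return times are available, state that they are an upper bound that also includes the STAI, the contact page, check-in and idle waiting; a client may hold a finished packet until called.

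If the sponsor does not intend to measure time, the alternative is to remove it from the Protocol Summary so that the summary matches the aims.

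The cost is minor clerical work on a packet that staff already hand out and collect, and one descriptive table. Clients enrolled before the change will lack times, so the summary will describe later enrollees only.

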**List of Abbreviations**

AE	Adverse Event/Adverse Experience
AI	Associate Investigator
DSMB	Data Safety and Monitoring Board
FWA	Federal Wide Assurance
ICF	Informed Consent Form
IRB	Institutional Review Board
GC	Genetic Counselor
HBOC	Hereditary Breast and Ovarian Cancer
N	Number (typically refers to number of subjects/sample size)
NCI	National Cancer Institute
NHGRI	National Human Genome Research Institute, NIH
NIH	National Institutes of Health
OHRP	Office for Human Research Protections
OHSRP	Office of Human Subjects Research Program
PI	Principal Investigator
SA	Self-Affirmation
SAE	Serious Adverse Event/Serious Adverse Experience
SI	Student investigator
SOP	Standard Operating Procedure
UP	Unanticipated Problem
UPnonAE	Unanticipated Problem that is not an Adverse Event

## 1.0 Precipis

The proposed study is a feasibility study to assess the viability of implementing a Self-Affirmation (SA) intervention in a Hereditary Breast and Ovarian Cancer (HBOC) genetic counseling clinic to improve client communication and behavioral outcomes. Participants will be clients and genetic counselors at the St. Luke's Hospital System and Medstar Washington Hospital Center HBOC clinics. This study seeks to identify outcomes that would be most informative in a large-scale research protocol. As outcomes, we will assess clients' decision self-efficacy, intention to talk with family, genetic test uptake, empowerment, and HBOC knowledge. We will also assess counselors and clients perceived benefits, perceived harms, and acceptance of the affirmation intervention.

In this study clients will be invited to participate in an intervention before their genetic counseling appointment. The SA intervention is a short written exercise to reinforce clients' self-integrity (a global sense of personal adequacy), leading to more openness to threatening information within the genetic counseling session. Clients and counselors will be surveyed after the study to assess outcome measures and feasibility of the intervention.

Social science research has shown that when people are faced with threatening information they often seek to protect themselves and reject the threatening message. Message rejection can include minimizing the importance or discrediting the truth of the message. SA interventions aim to bolster self-integrity by focusing on aspects of subject's lives they value and thereby improving participants' self-perception and tolerance towards threatening messages. SA manipulations have been shown to increase patient communication within appointments and both intentions and actions toward behavior change.

Often in cancer genetic counseling appointments clients are confronted with the threat of having a significantly increased risk of cancers while being asked to make a decision about genetic testing. A self-affirmation intervention may facilitate greater client decision self-efficacy, empowerment, and positive behavior outcomes, such as communication with family regarding genetic risk and screening behaviors.

## 2.0 Objectives and specific aims

The objective of this study is to investigate if a self-affirmation intervention is feasible in the context of HBOC genetic counseling appointments.

### Specific aims

1. To assess the preliminary impact of a SA intervention on outcomes that may be implemented in future studies, by assessing differences in the following between a SA intervention and unaffirmed standard SA control group of HBOC genetic counseling clients:
  - a. Intentions to talk with family, test uptake
  - b. Empowerment, decision self-efficacy
  - c. HBOC knowledge
2. To describe genetic counselors' (GCs) and clients' response to a novel, client-based SA intervention, including perceived impact, barriers, and facilitators to implementing such an intervention on a wider scale

3. To assess the percentage of eligible clients that completed a pre-visit SA intervention and if the SA intervention is effective in affirming clients.

### 3.0 Brief rationale and background

Breast cancer is the most prevalent cancer in women, with 230,815 new diagnoses in women in 2013 alone (U.S. Cancer Statistics Working Group, 2016). It is estimated that 5-10% of women with breast cancer and 20% of women with ovarian cancer carry a gene variant that predisposes them to these cancers (Campeau et al., 2008; Walsh et al., 2011). Being at genetic risk for cancer means clients often face difficult decisions about testing, conversations with family members, prophylactic surgery, and preventative medications. As more people are faced with these decisions it is important to understand how to best aid them in the decision-making process. Self-affirmation has shown to increase patient engagement and problem solving. This proposed study is a feasibility, randomized control trial to assess the initial outcomes of self-affirmation and the openness of genetic counselors and clients to an intervention for improving clients' genetic counseling experiences and outcomes.

#### **Self-affirmation.**

Self-affirmation (SA) theory suggests that people work to maintain their perceptions of self-integrity, morality, and consistency (Sherman & Cohen, 2006; Steele, 1988). When they experience a threat to the self-concept they seek to neutralize it through defending themselves against the message. Self-integrity is an individual's perception of their efficacy across multiple domains, defined further as their cumulative moral and adaptive adequacy (Steele, 1988). Self-integrity can be best understood in context. For example, a woman may feel threatened by a negative health finding, but if she feels competent in her relationships, then her overall self-integrity is likely to be maintained and she can address the threat in a non-defensive manner. On the other hand, when self-integrity is compromised, and other areas of self-concept do not stabilize the threat, then individuals can become defensive against the threatening message to protect their self-integrity (Sherman & Cohen, 2006; Steele, 1988). For example, they may try to discredit or ignore a concerning message.

SA theory further postulates that an affirmation intervention prior to facing a threat can reinforce an individual's self-integrity and increase openness to the threat (e.g., a threatening message or performance in a difficult task; Sherman & Cohen, 2006). SA has also been shown to increase openness to threatening health messages. In one study, 66 women were given an article stating that coffee consumption increases the risk for fibrocystic breast disease (Reed & Aspinwall, 1998). Half of the women were given a self-affirmation measure focusing on kindness before reading the article. Those who drank coffee and were self-affirmed oriented to and accepted risk confirming information significantly more quickly than did coffee drinkers who were un-affirmed. Other studies have shown similar results related to accepting threatening health messages (Harris & Epton, 2009).

Specific to genetic information, SA has been shown to improve openness. One survey of 594 participants in the ClinSeq cohort found that those who were higher in spontaneous self-affirmation were more likely to intend to seek out genetic risk information despite being high in anticipated affect, a correlate for worry (Ferrer et al., 2014). SA may affect people's desire for genetic test results. SA may increase clients' likelihood to talk with family members about genetic information. Not telling relatives could have negative outcomes for at-risk family members. Ferrer and colleagues' (2014) ClinSeq research found that those who were higher in spontaneous SA were significantly more likely to intend to share actionable genetic testing

results ( $p = 0.05$ ) and non-actionable results ( $p = 0.01$ ) with family members. Although spontaneous SA is distinct from prompted SA, this finding could suggest that an intervention would also increase discussions with family members. Additionally, SA interventions have been shown to significantly increase participants' feelings of love and connectedness to others compared to a control group, which may also be related to intentions to talk with family (Crocker, Niiya, & Mischkowski, 2008).

SA has also been shown to improve problem solving in stressful situations. A case-control study of 73 university students found that chronically stressed students who were self-affirmed before a remote associate problem-solving task (RAT) performed better than those who were chronically stressed and unaffirmed (Creswell et al., 2013). Both the main effect of SA ( $p = 0.005$ ) and the interaction effect between chronic stress and SA ( $p = .041$ ) were significant.

A meta-analysis of SA and responses to health messages assessing both intentions and behaviors in 16 studies found that aggregate effect sizes for health intentions and health behaviors were statistically significant but low at  $d = 0.26$  and  $d = 0.27$  respectively (Sweeney & Moyer, 2015). Behaviors and health intentions in this study were both negative (e.g. reducing caffeine intake or alcohol consumption) and positive (e.g. increasing sunscreen or condom use). It should be noted that 12 of the 16 studies reviewed used student samples where the threat was either far off (e.g. sunscreen use and skin cancer) or not personalized so the perceived threat of the message may have been low. In the proposed study the risk for HBOC cancer is personalized by family history or personal early onset cancer and the threat of cancer is either immediate or high. Since stress and heightened risk appraisals appear to moderate the effect of SA as an intervention, we would expect the effect of SA in this population to be higher than those in the meta-analysis.

Other studies have addressed SA and client engagement in a medical encounter. A randomized controlled trial of SA in African American clients with hypertension found that the SA treatment group requested and provided more information about their medical condition from their primary care provider in a medical encounter. Additionally, in the SA group, the patient-provider communication was characterized as being more interested, friendly, responsive, interactive, and respectful (Havranek et al., 2012). Since SA is postulated to increase message acceptance and to decrease motivation to avoid the threat, it is consistent that clients may attend to the threatening message more carefully and remember information about HBOC more accurately (Harris & Epton, 2009).

SA is postulated to decrease patient defensiveness. To our knowledge there are no direct measures of patient defensiveness but this construct has been assessed by measuring numerous downstream constructs in past research, including perceived threat, message acceptance, and defensive avoidance (Good & Abraham, 2007). In this study, we will be measuring the downstream effects of defensiveness by assessing patient empowerment and decision efficacy. SA interventions are theorized to decrease patient defensiveness, which will increase their openness to threatening information, which will increase decision self-efficacy. Furthermore, increased openness will increase the client's engagement in the genetic counseling session and result in greater patient empowerment. It is also possible that client self-integrity, their global sense of personal adequacy, is related to empowerment more directly than outlined above.

